Ucak, 2011 [46]	40	CABG, adults	PBO vs Gaba 1200 preop and x2d	pain (at rest and coughing), tramadol use	+	Gabapentin significantly reduced the intensity of pain and tramadol consumption in the early postoperative period after CABG surgery. Pain scores at 1 and 3 months after surgery were low in both groups, with no significant difference between the groups.
Spence, 2011 [47]	70	Shoulder arthroscopy, adults	PBO vs Gaba 300mg preop then BID x2d	Average pain scores; opioid consumption, AE, sleep	-	No analgesic benefit
Ghai, 2011 [48]	90	Abdominal hysterectomy, adult women	PBO vs Gaba 900 vs 300 Pregaba preop	Analgesic consumption x24h; pain scores, time to rescue analgesia	+	Significantly lower analgesic consumption for both Gaba and Pregaba vs placebo; Pain scores lower for first hour then no differences; rescue analgesia time lowest for pregaba then gaba then PBO.
Khan, 2011 [49]	175	lumbar laminectomy, adults	7 groups: 600, 900, 1200mg gaba preop vs postop vs PBO	Morphine consumption, time to rescue analgesia, pain scores	+	Gabapentin 900 or 1200 mg, administered either pre- or post-incision, was found to be effective in pain management following lumbar laminectomy. Similar doses of gabapentin provide the same post-operative analgesia whether administered pre- or post-incision.
Moore, 2011 [50]	46 (44)	Cesarean delivery, adult women	PBO vs Gaba 600mg	Pain scores, satisfaction, opioid consumption, side effects; neonatal interventions	+	Preoperative gabapentin 600 mg in the setting of multimodal analgesia reduces postcesarean delivery pain and increases maternal satisfaction in comparison with placebo. Opioid consumption did not differ.

Author, Year [Reference]	n (analyzed)	Population	Intervention	Outcome measure	Results
Syal, 2010 [51]	120	Open cholecystectomy, adults	4 groups: PBO, APAP 1000mg, Gaba 1200mg, APAP + Gaba; administered preop	Rescue analgesic (time, number, and total amount); pain score (rest and mvmt)	+ Group 3 had lower pain scores at rest and on movement at all time intervals in comparison to the Group 1. Similarly Group 4 had lower pain scores at rest and on movement at all time intervals in comparison to the Placebo Group. Patients who consumed Gabapentin alone had lower scores at all time intervals in comparison to Group 2 but the difference in resting score was statistically significant only at 0, 1, 2 and 24 hours post-operatively while movement score was statistically significant at all time intervals except at 6 hours
Bang, 2010 [52]	46	Arthroscopic rotator cuff repair, adults	PBO vs Gaba 200mg preop	Pain scores; opioid consumption and side effects	+ Significant decrease in pain scores, no difference in opioid consumption
Amr, 2010 [53]	150	Partial or radical mastectomy, adult women	PBO vs Gaba 300mg/d vs venlafaxine 37.5 mg/d	Pain scores, analgesic requirements	+ Pain after movement was reduced by gabapentin from the second to tenth postoperative day but no difference was found regarding pain during rest. Gabapentin reduced morphine consumed in the first 24 hours postoperatively. The analgesic requirements from the second to tenth days were reduced compared to the control group.
Rapchuk, 2010 [54]	60	Cardiac surgery, adults	PBO vs Gaba 1200mg preop and 600mg BID x2d	Postop opioid, pain, sleep, pt satisfaction	none No differences
Rusy, 2010 [11]	59	Spinal fusion, Pediatric	PBO vs Gaba 15mg/kg preop and 5mg/kg TID	total morphine consumption, pain scores	+ Significantly less morphine used, reduced pain scores initially.

There is emerging evidence that patients with SCD experience neuropathic pain as a component of their acute pain episodes. Allodynia and hyperalgesia are symptoms commonly experienced by patients with SCD and are defining characteristics of neuropathic pain [55]. In one survey of adult patients seen at a SCD specialty clinic, 90% of 145 patients verbalized pain descriptors consistent with neuropathic pain [56]. Another evaluation of 56 SCD patients age  $\geq 14$  years revealed that 40% experienced definite or probable neuropathic pain. Only 4% of patients were receiving treatment directed at neuropathic pain [57]. No formal studies have been completed using gabapentin in patients with SCD.

Based on the evidence suggesting that patients with SCD experience neuropathic pain, the analgesic benefit of gabapentin demonstrated in the acute pain setting, and the limited length of time that patients stay in the acute care setting for pain management for VOC, we propose an intervention consisting of a single dose gabapentin of 15 mg/kg, as soon as possible after presentation to the hospital, in addition to the current standard of practice which includes the use of an opioid and a non-steroidal anti-inflammatory drug for pain in VOC.

Age-appropriate pain assessment tools are used in our institution as per the pain standard of care: the Faces, Legs, Arms, Cry and Consolability (FLACC) pain scale for children younger than 4 years [58], Wong Baker FACES for children 4 to 6 years [59, 60], and NRS for those 7 years or older [61, 62]. The FLACC scale is a 5 item scale that raters use to score each of the 5 categories: F (faces), L (legs), A (activity), C (cry), and C (consolability), which are scores from 0 to 2 (Merkel 1997). The reliability and validity data on the FLACC tool are extensive [58, 63-65].

The Wong Baker FACES is a horizontal scale of 6 hand-drawn faces, now scored from 0 to 10, that range from a smiling “no hurt” face on the left to a crying “hurts worst” face on the right [60]; faces pain scales have been used in numerous to measure acute, procedural and recurrent pain, as reported in a systematic review of faces scales for the self-report of pain intensity in children[66]. The Wong Baker FACES has adequate psychometric properties, and it is easy and quick to use [60, 66, 67] and inexpensive to reproduce. The greatest strength of this is its acceptability; studies have consistently found that the WBFPRS was preferred by children of all ages, parents, and practitioners, when compared with other faces pain scales[68-70]. In a systematic review of the psychometric properties, interpretability and feasibility of self-report pain

intensity measures for use in clinical trials in children and adolescents, the Wong Baker FACES, is reported to have reliability, validity, high feasibility, and responsiveness in terms of detecting change in children's pain intensity for ages 3 to 18 years[67].

## 2.2 **Rationale**

An extensive literature review is presented in section 2.1, in support of the clinical relevance of gabapentin, particularly in the setting of acute nociceptive pain.

Our hypothesis is that the addition of gabapentin to the current standard regimen of non-steroidal anti-inflammatory drugs and opioids, in the ACS of VOC-related pain, will improve the quality of pain control. The rationale supporting this expected effect includes the following:

- a. The concept of “rational poly-pharmacy”, which supports the concurrent use of drugs with distinctly different mechanisms of action to produce analgesia [30, 71]. Gabapentin-related analgesia is based on a different mechanism of action (at the  $\alpha$ -2- $\delta$  subunit of the voltage-dependent calcium channel) than opioid analgesia (mu opioid receptor agonist effect) and non-steroidal anti-inflammatory drugs (cyclooxygenase inhibition);
- b. Proven analgesic efficacy in the acute pain setting of postoperative pain in adults [13, 14] and children [11]. Additional evidence is provided in the literature review section of the background, based on 43 references.
- c. Evidence that one of the mechanisms of acute pain in the VOC may be a neuropathic mechanism, based on demonstration of hyperalgesia and allodynia in animal models of sickle cell disease [72, 73]; hyperalgesia and allodynia are clinical characteristics of neuropathic pain;
- d. Evidence that the combination of opioid and gabapentin is more effective than either one intervention alone, in the context of chronic pain [30];

Repetitive VOC events and associated acute pain episodes, like any other repetitive pain events, may contribute to the development of neuroplasticity and central sensitization. The neuronal phenomena of neuroplasticity and central sensitization are responsive to therapy with gabapentin [74-78]. Furthermore, there is evidence from animal studies that gabapentin is more effective in modulating nociceptive transmission in the presence of inflammation [74] and central sensitization [75], and the potency of the

antinociceptive effect is directly related to the intensity of sensitization [76]. The presence of both phenomena of inflammation and neuropathic pain mechanisms has been supported by the finding of neurochemical changes in the spinal cord and peripheral nerves in the transgenic sickle mouse model [73], and pain has been found to be related to a mechanism of ischemia and reperfusion injury, which exacerbates hyperalgesia [72]. Based on the contribution of neuroplasticity and central sensitization in the development of pain in repetitive VOC episodes [12] and the evidence of efficacy of gabapentin in modulating nociceptive mechanisms associated with inflammation and central sensitization, we expect an intervention with gabapentin for VOC pain to provide analgesic efficacy.

### **3.0 RESEARCH PARTICIPANT ELIGIBILITY CRITERIA AND STUDY ENROLLMENT**

According to institutional and NIH policy, the study will recruit research participants regardless of gender and ethnic background. Institutional experience confirms broad representation in this regard.

#### **3.1 Inclusion Criteria**

- 3.1.1 Participant must have sickle cell disease (any genotype), documented in the St. Jude medical record.
- 3.1.2 Participant must be seeking care for acute vaso-occlusive pain at St. Jude Children's Research Hospital.
- 3.1.3 Participant age must be  $\geq 1$  year and  $< 21$  years.

#### **3.2 Exclusion Criteria**

- 3.2.1 Prior randomization in this study.
- 3.2.2 Mild pain (score  $< 4$ ), or pain for which treatment with opioid is not indicated.
- 3.2.2 Pregnant or lactating females.
- 3.2.3 Decreased GFR ( $< 60 \text{ml/min}/1.73\text{m}^2$ ) as estimated by the revised Schwartz equation.
- 3.2.4 Current treatment with gabapentinoid drugs (gabapentin or pregabalin).
- 3.2.5 Known seizure disorder.
- 3.2.6 Current treatment with antiepileptic agents.

- 3.2.5 Pain in combination with other clinical symptoms that require additional interventions, including fever with focus, acute chest syndrome, acute injury, or splenic sequestration.
- 3.2.6 Allergy to gabapentin.
- 3.2.7 Current participation in another research study with an IND/IDE agent (including SCATE and TWiTCH trials).
- 3.2.8 Inability or unwillingness of research participant or legal guardian/representative to give written informed consent.

### **3.3 Research Participant Recruitment and Screening**

St. Jude patients with sickle cell disease will be educated about the availability of this study by study staff or hematology staff as appropriate during routine visits to the clinic. Informational flyers will be available for distribution (Appendix III). Providing information to patients and family in advance of an acute pain crisis should assist in the informed consent process by giving patients the opportunity to ask questions and consider options prior to a qualifying pain event.

Potentially eligible patients will be referred to the study team from the primary clinical team (Hematology Service) when the patient calls or arrives at the acute care setting with complaint of vaso-occlusive pain crisis. With the agreement of the primary clinical team, a study team member will approach the patient to initiate/continue informed consent discussions while standard pain management workup is ongoing.

When informed consent is obtained and the patient is enrolled, a member of the study team will inform the pharmacy and the randomization procedure will be initiated. The pharmacy order sets will be activated for the study drug. Delegated clinicians will order the study drug as per protocol section 4.0.

### **3.4 Enrollment on Study at St. Jude**

A member of the study team will confirm potential participant eligibility as defined in Section 3.1-3.2, and will complete and sign the 'Participant Eligibility Checklist'. The study team will enter the eligibility checklist information into the Patient Protocol Manager (PPM) system. Eligibility will be reviewed, and a research participant-specific consent form and assent document (where applicable) will be generated. The complete signed

consent/assent form(s) must be faxed or emailed to the CPDMO at [REDACTED] to complete the enrollment process.

The CPDMO is staffed 7:30 am-5:00 pm CST, Monday through Friday. A staff member is on call Saturday, Sunday, and holidays from 8:00 am to 5:00 pm. Enrollments may be requested during weekends or holidays by calling the CPDMO “On Call” cell phone [REDACTED] or referencing the “On Call Schedule” on the intranet).

### **3.5 Procedures for Identifying and Randomizing Research Participants**

Eligibility of research participants will be confirmed between the study staff and treating clinician from the Hematology service. A member of the study team will then approach the patient and the legally authorized representative regarding the study. If the research participant and/or parent agree to participate, the randomization plan established by the study biostatistician will be accessed according to Section 11.2.

## **4.0 TREATMENT PLAN**

### **4.1 Treatment**

Upon each participant’s enrollment, study staff will randomize the participant to one of 2 possible treatment arms (see section 11 for randomization procedure) and order the study treatment. The pharmacy will dispense the dose of study treatment ( gabapentin vs. placebo) to the clinic or medicine room as soon as possible.

Study drug and other interventions will be administered and documented according to hospital policy by any appropriate clinical staff. All caregivers and study personnel will be blinded to the treatment assignment. Based on previous research experience at St. Jude, administration of the study drug is estimated to occur no later than 2 hours after patient’s first opioid pain medication in the acute care setting.

### **4.2 Dose Modifications**

Medication dosing may be modified for research recipients based upon actual body weight or adjusted ideal body weight when clinically indicated. Criteria

for medication calculations based on body weight/body surface area can be found in any version of the St. Jude Formulary. Medication doses may be rounded to the nearest integer or to the nearest appropriate quantity when clinically or pharmaceutically indicated as per the MD and PharmD.

The maximum dose is 900mg.

#### **4.3 Concomitant Therapy**

It is expected that participants in this study may be receiving concomitant therapies unrelated to the primary interests of this study. Only the study treatment and IV administered pain control treatments will be analyzed to determine the study outcomes. Patients on long-term treatments for sickle cell disease (e.g. hydroxyurea or chronic transfusion therapy) will be recorded for analysis.

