### 1.2 **Secondary Objective**

To compare the total morphine equivalent dose (mg/kg) used to control pain during VOC between presentation to the acute care setting and assessment at 3 hours post administration of study drug in the gabapentin vs. placebo groups.

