### 1.3 **Exploratory Objectives**

- 1.3.1 To assess the analgesic efficacy of gabapentin (vs. placebo) for pain during VOC in participants with SCD, as defined by a decrease in pain scores of  $\geq 33\%$  between presentation to the acute care setting and the point of decision for either hospital admission or discharge to home, in the gabapentin and placebo groups.
- 1.3.2 To compare the total morphine equivalent dose (mg/kg) used to control pain during VOC between presentation to the acute care setting and the point of decision for either admission or discharge to home, in the gabapentin and placebo groups.
- 1.3.3 To compare the rate of admission related to pain management, in the gabapentin vs. placebo groups.
- 1.3.4 To compare the change in pain score from time of administration of study drug to assessment at 3 hours post administration of study drug in the gabapentin vs. placebo groups.
- 1.3.5 To compare the change in pain score from time of administration of study drug to the point of decision for either admission or discharge to home, in the gabapentin and placebo groups.

Figure 1. Pain Assessment Time Points and Study Objectives

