## **6.2 Evaluations During Therapy**

Data for research purposes will be collected from the hospital medical records for the event, including visit duration, pain scores, and IV administered pain interventions given, as performed according to hospital standards of care. Only St. Jude pharmacists are unblinded to treatment assignment.

Pain assessments throughout the acute event will be performed by any clinical staff as per hospital standards (Appendix II). Researchers will analyze pain scores at baseline (at presentation), 15 minutes prior to or 15 minutes after the time of study drug administration, at 3 hours after study drug administration, and at point of decision for either admission or discharge to home (for patients who continue to be treated for pain longer than 3 hours after study drug is administered).

The pain scales used are the numerical rating system, the Faces Pain Scale, and the FLACC pain scale (for patients 7 years or older, ages 4-6 years, or less than 4 years, respectively) (Appendix II). Patients unwilling or unable to provide a score on the age-appropriate scale may use another scale if indicated.

Clinicians will obtain other studies as needed for good patient care.

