## 7.0 EVALUATION CRITERIA

### 7.1 Response Criteria

The response to therapy will be measured by pain intensity scores and total opioid use as described in the study objectives.

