## 11.2 Randomization

Eligible patients with an established diagnosis of pain and VOC will be consented and randomized to receive a single dose of gabapentin or placebo. Morphine or other opioid and non-steroidal anti-inflammatory drugs will be available to both groups as needed for pain and will be administered according to the current standard of care for pain in VOC from the Department of Hematology. Randomization will be performed in SJCRH pharmacy by a pharmacist, using the randomization program developed by the Department of Biostatistics. The randomization will be stratified by three age categories (1-3yr, 4-6yr,  $\geq 7$ yr) for which distinct pain assessment tools are applied and for 2 pain scores categories at assessment at presentation: 4- 6 and 7-10, respectively. A

block randomization with block sizes varying randomly between 4 and 6 will be used in each stratum.

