#### **11.3.2 Secondary Objective**

To compare the total morphine dose or morphine equivalent (mg/kg) used to control pain during VOC between presentation to the acute care setting and assessment at 3 hours post administration of study drug in the gabapentin vs. placebo groups.

Summary statistics of the total morphine dose or morphine equivalent (mg/kg) used to control pain during VOC between presentation to the acute care setting and 3 hours post administration of study drug, in the gabapentin and placebo groups will be provided. Test of normality such as Shapiro-Wilk test will be applied to the total morphine dose or morphine equivalent (mg/kg) to examine their deviation from the normal distribution. A two-sample t-test or Wilcoxon rank sum test will be used to compare the total morphine dose or morphine equivalent (mg/kg) for the gabapentin vs. placebo groups depending on whether the normality assumption of the data holds.

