#### **11.3.3 Exploratory Objectives**

1. To assess the analgesic efficacy of gabapentin for pain during VOC in participants with SCD, as defined by a decrease in pain scores of  $\geq 33\%$

between presentation to the acute care setting and the point of decision for either hospital admission or discharge to home, in the gabapentin and placebo groups.

Statistical methods used to analyze this objective will be the same as those used for the primary objective.

2. To compare the total morphine dose or morphine equivalent (mg/kg) used to control pain during VOC between presentation to the acute care setting and the point of decision for either admission or discharge to home, in the gabapentin and placebo groups.

Statistical methods used to analyze this objective will be the same as those used for the secondary objective.

3. To compare the rate of admission related to pain management, in the gabapentin vs. placebo groups.

Statistical methods used to analyze this objective will be the same as the analysis used for the primary objective.

4. To compare the change in pain score from time of administration of study drug to assessment at 3 hours post administration of study drug in the gabapentin vs. placebo groups.

The numeric changes in pain scores will be compared using the statistical methods of the secondary objective. Changes in pain score will also be evaluated as a proportion of those with a decrease of  $\geq 33\%$  and analyzed by the methods of the primary objective.

5. To compare the change in pain score from time of administration of study drug to the point of decision for either admission or discharge to home, in the gabapentin and placebo groups.

The numeric changes in pain scores will be compared using the statistical methods of the secondary objective. Changes in pain score will also be evaluated as a proportion of those with a decrease of  $\geq 33\%$  and analyzed by the methods of the primary objective.

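### Section 4.3 restricts the analysis to IV pain treatments, but the only secondary outcome is a total morphine-equivalent dose with no limit by route, so oral opioid would count as zero

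*Combined protocol and SAP*

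**What the plan says.** Two sections point to intravenous treatment only:

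- Section 4.3: "Only the study treatment and IV administered pain control treatments will be analyzed to determine the study outcomes".
- Section 6.2, describing the data taken from the hospital record, names "visit duration, pain scores, and IV administered pain interventions given". The list is introduced as examples, so it does not strictly exclude other data.

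The sections that define the dose outcome name no route:

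- Section 1.2, the only secondary objective: "To compare the total morphine equivalent dose (mg/kg) used to control pain during VOC", from arrival to 3 hours after study drug.
- Section 1.3.2, exploratory: "total morphine equivalent dose (mg/kg) used to control pain during VOC between presentation to the acute care setting and the point of decision".
- Section 7.1: "The response to therapy will be measured by pain intensity scores and total opioid use as described in the study objectives".
- Section 11.3.2: "Summary statistics of the total morphine dose or morphine equivalent (mg/kg) used to control pain during VOC", followed by a t-test or Wilcoxon rank sum test according to a normality check.
- Section 11.3.3, for the exploratory dose objective: "Statistical methods used to analyze this objective will be the same as those used for the secondary objective".

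On what patients may receive, section 11.2 says: "Morphine or other opioid and non-steroidal anti-inflammatory drugs will be available to both groups as needed for pain". It gives no route. The Protocol Summary (Brief Outline of Treatment Plan) says that further pain medicine may be intravenous or oral.

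**The concern.** The dose outcome has two definitions that cannot both be followed. An abstractor or analyst who works from section 4.3 leaves oral opioid out of a quantity labelled as a total. One who works from section 11.3.2 includes it and departs from section 4.3. No section reconciles the two.

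The choice matters because route after randomization is decided in the course of care. If gabapentin changes pain, it may change when staff move from IV to oral treatment. An IV-only count would then record a change of route as opioid sparing, or would hide a real saving. Blinding and randomization balance the arms at entry, but they do not hold route constant afterwards. Opioid dose is the trial's only secondary outcome, and any opioid-sparing claim would rest on it.

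**Working it through.** The documents give no oral share, mean dose, SD or power for the opioid outcome, so there is no planned figure to reproduce. The check has two parts: a reading of the text, and an illustration under stated assumptions.

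**Reading of the text**

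1. The rule in section 4.3 is exclusive and is tied to the study outcomes, so it covers the dose outcome.
2. Sections 1.2, 1.3.2, 7.1, 11.3.2 and 11.3.3 neither name a route nor refer back to 4.3.
3. Oral opioid is not barred. Section 4.4 lists opioid as part of standard care without a route, section 11.2 does the same, and the Protocol Summary allows oral pain medicine, though it does not name oral opioid.
4. Under section 4.3 as written, an oral opioid dose given inside the window therefore contributes nothing to the total.

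**Illustration**

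Let s_G and s_P be the oral shares of the true morphine-equivalent total on gabapentin and placebo. Then:

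IV-only ratio = true ratio × (1 − s_G) / (1 − s_P)

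*Equal shares s.* The factor is 1, so the ratio of means is unchanged, and the absolute difference is multiplied by (1 − s). Take assumed true means of 0.30 mg/kg on placebo and 0.24 mg/kg on gabapentin (difference 0.06, ratio 0.80):

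| s | IV-only difference (mg/kg) | Ratio |
|---|---|---|
| 10% | 0.06 × 0.90 = 0.054 | 0.80 |
| 20% | 0.06 × 0.80 = 0.048 | 0.80 |
| 30% | 0.06 × 0.70 = 0.042 | 0.80 |

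If the share is also the same for every patient, all doses are multiplied by one constant, and the t statistic and the Wilcoxon ranks do not change. In that case only the estimate in mg/kg is understated.

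*Unequal shares, equal true totals (true ratio 1):*

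| s_P | s_G | IV-only ratio | Apparent change |
|---|---|---|---|
| 10% | 20% | 0.8/0.9 = 0.889 | −11.1% |
| 20% | 30% | 0.7/0.8 = 0.875 | −12.5% |
| 20% | 40% | 0.6/0.8 = 0.750 | −25.0% |
| 20% | 10% | 0.9/0.8 = 1.125 | +12.5% |

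*A real effect hidden.* With a true ratio of 0.889 and shares of 20% on placebo and 10% on gabapentin, the IV-only ratio is 0.889 × 1.125 = 1.00. A true 11.1% reduction disappears.

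All shares and doses here are assumptions.

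**The case against.** The strongest reply is that section 4.3 defines the outcome rather than conflicting with it. On that reading, the word total in the objectives means summed over the time window, section 6.2 confirms the IV limit, and the only defect is a label that omits IV. This reading is possible, but it still leaves sections 1.2, 1.3.2, 7.1 and 11.3 promising something other than what is measured, so the text needs correcting either way.

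Several other points stand and limit the finding:

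- Section 6.2 does not exclude oral data, and section 10.1 has data abstracted from the electronic record. Oral doses may therefore be recoverable; counting them as zero follows only from applying 4.3 literally.
- The Protocol Summary speaks of pain medicines in general, which could mean oral NSAIDs, and it is not tied to the 3-hour window. Oral opioid use inside the window is permitted by silence but is not documented.
- Staff are blinded, and nothing in the documents shows that route would differ by arm. Opioid given between arrival and randomization is inside the window, and its route cannot depend on arm.
- The longer window of 1.3.2 leaves more room for oral dosing, but only for patients treated beyond 3 hours. Under Appendix I, patients who leave at 3 hours have no later assessment.

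**Conclusion.** The concern holds. Section 4.3 sets an IV-only rule for the study outcomes, while the sections defining the dose outcome set no limit by route, and nothing in the documents settles which governs. This is a conflict between stated rules, not a missing detail.

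Confidence is high for the contradiction. The size of any bias is unknown and could be nil, because it depends on oral shares that the documents do not give. If the shares are equal, the mg/kg difference shrinks by that share and the ratio stands. If they differ by ten percentage points in the ranges illustrated, the spurious change is about 11% to 13%, in either direction. The exploratory outcome in 1.3.2 has the same fault.

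The primary endpoint uses pain scores only, so it, the sample size of 166, the interim boundaries and the type I error rate are untouched. The point should be fixed before the opioid outcome is analysed.

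**What to change.** Preferred: amend sections 4.3 and 6.2 so that opioid doses by every route are abstracted, from arrival to 3 hours after study drug and to the decision on admission or discharge. Convert them to morphine equivalents per kg with a prespecified table. Use that total in section 11.3.2 and in exploratory objective 2 of section 11.3.3, and report the IV-only total as a sensitivity analysis.

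Alternative, if IV-only was intended: restate sections 1.2, 1.3.2, 7.1 and 11.3 as IV opioid dose, and limit any opioid-sparing conclusion to IV opioid.

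The first option costs a little extra abstraction from the electronic record that section 10.1 already uses, plus one conversion table. The second is a change of wording only, but it answers a narrower question. Both concern measurement and analysis; neither adds a study procedure or alters treatment.
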